## **Day 60**

- AEs
- Follow-Up (Telemed).

### **5.4.3. Visit Schedule Part 2**

AEs and concomitant medications will be reviewed and documented every day of hospitalization. Monitoring is to be conducted daily if no continuous monitoring is available, unless specified below.

## **Day 1**

### *Prior to infusion start*

- Conduct final determination of eligibility prior to the start of USB002/placebo infusion.
- If not done in previous 72 hours, repeat within 24 hours of start of infusion:
  - Physical exam (for eligibility only, does not need repeating);
  - Laboratory sample collection per Section 5.2;
  - Respiratory assessments per Section 5.3;
  - Vitals;
  - 12 lead-ECG;
  - Chest X-ray (for eligibility only, does not need repeating);
  - Pregnancy test;
  - OSCI assessment.

### **Day 1 - 0 hours**

- Infusion start: As soon as possible once deemed eligible.

### **Days 1-14**

- Blinded Dosing
- Vitals;
  - If no continuous vitals monitoring, collect vital signs per Section 5.3 during the infusion period.
- Respiratory assessments per Section 5.3;
- Laboratory (chemistry, hematology, coagulation and urinalysis [Day 1 only] per Section 5.2);
- 12 lead-ECG (Day 1);
- SBT and at any time that weaning criteria is met;
- OSCI (Day 7);
- AEs;
- Concomitant medications.

**Day 16** (End of Treatment or Early Termination of Treatment)

- Laboratory assessments (chemistry, hematology, coagulation and urinalysis per Section 5.2);
- 12 lead-ECG;
- Vitals;
- Respiratory assessments per Section 5.3;
- SBT and at any time that weaning criteria is met;
- OSCI assessment;
- AEs;
- Concomitant medications.

**Days 18, 21, 24, 28**

- Laboratory (chemistry, hematology, coagulation per Section 5.2);
- OSCi assessment (Day 28);
- AEs;
- Concomitant medications;
- Follow-Up (Telemed) (Day 28).

**Day 60**

- AEs;
- Follow-Up (Telemed).

**5.4.4 End of Treatment or Early Termination of Treatment**

Subjects completing the study up to Visit 5 (in Part 1) or Day 16 (in Part 2) will have End of Treatment procedures completed at Visit 5 (in Part 1) or Day 16 (in Part 2). For subjects discharged prior to Visit 5 (in Part 1) or Day 16 (in Part 2) or where treatment is terminated early, for any reason, all attempts will be made to conduct the End of Treatment (Visit 5 or Day16) procedures (See Tables 2 and 3). End of Treatment (Visit 5 or Day16) procedures may be conducted during the 24-hour observation period.

See Section 5.4.2 Visit 5 (Part 1) and Section 5.4.3 Day 16 (Part 2).

**5.4.5 Hospital Discharge Prior to Day 28**

If a subject is discharged from hospital earlier than Day 28, Telemed visits will be conducted once a week until Day 28, with the first occurring approximately 7 days after discharge. The Day 28 and Day 60 Telemed visits will occur on Days 28 and 60, respectively, regardless of when the subject is discharged from hospital and the timing of their previous weekly Telemed visits. Part 1 subjects discharged prior to Day 28 will not return to the site for visits (may apply to any of Days 7, 9, 12, 14, 16, 18, 21, or 24, depending on day of discharge) or undergo the procedures regularly scheduled for those visits. Part 2 subjects discharged prior to Day 28 will not return to the site for visits (may apply to Days 18, 21, or 24, depending on day of discharge) or undergo the procedures regularly scheduled for those visits.

Data from the Telemed visits post-discharge will be captured in the EDC.

**Table 2. Schedule of Assessments: Part 1**

Assessments		Timepoint																							
		Screening (72 hours)					Visit 1			Visit 2			Visit 3	Visit 4	Visit 5	Day								+/- 7 days	
							0 hrs 	4 hrs	8 hrs	12 hrs	24 hrs	32 hrs	40 hrs	48 hrs		72 hrs	96 hrs	7 	9 	12 	14 	16 	18 	21 	24 
Informed Consent	X																								
Medical and Surgical History 	X																								
Demographics	X																								
Physical exam 	X	X																							
Chemistry	X	X					X					X	X	X	X				X			X		X	
Hematology	X	X					X					X	X	X	X				X			X		X	
Coagulation	X	X					X					X	X	X	X				X			X		X	
Urinalysis	X	X														X									X
Pregnancy test	X	X																							
12-lead ECG	X	X										X	X	X	X		X	X			X				
Chest X-ray	X	X																							
Vital signs	X	X	X	X	X	X	X	X	X	X	X	X	X	X	X	X	X	X	X	X	X	X			
SBT Assessment							X					X	X	X	X		X	X	X	X	X	X			
Respiratory assessments	X	X	X	X	X	X	X	X	X	X	X	X	X	X	X	X	X	X	X	X	X	X			
Blinded Dosing		X	X	X	X	X	X	X	X	X	X	X	X	X	X										
OSCI Status	X	X															X								X
Adverse Events		X	X	X	X	X	X	X	X	X	X	X	X	X	X	X	X	X	X	X	X	X	X	X	
Concomitant Medication	X	X	X	X	X	X	X	X	X	X	X	X	X	X	X	X	X	X	X	X	X	X	X	X	
Follow-Up  (Telemed)																								X	X

1. History to include but not limited to any significant, ongoing, or controlled with treatment, medical condition; date of hospital admission; date of ICU admission; start time of supplemental oxygen therapy; start time of nasal high-flow oxygen therapy; start time of non-invasive mechanical ventilation or mechanical ventilator via intubation.
2. If screening assessments are not completed prior to start of infusion, conduct within 24 hours of infusion start. If performed as part of screening and within 72 hours, do not repeat unless required by the Investigator. Chest X-ray and Physical Exam do not need repeating within 24 hours.
3. Physical exam to include lung auscultation.
4. Visit 5 is also End of Treatment – all End of Treatment assessments are to be conducted at Visit 5 for all subjects or for any discharge prior to Visit 5.
5. If subject is discharged from hospital, Telemed visits will be conducted once a week until Day 28, with the first occurring approximately 7 days after discharge. Day 28 and Day 60 Telemed visits will occur on Days 28 and 60, respectively, regardless of discharge date and timing of previous Telemed visits. Discharged subjects will not attend the site for visits (Days 7, 9, 12, 14, 16, 18, 21, or 24, as applicable to discharge day) or undergo procedures scheduled for those visits.
6. Telephone follow-up, if discharged. Day 28 phone call window = +/- 3 days; window not applicable if still hospitalized.

**Table 3. Schedule of Assessments: Part 2**

Assessments	Timepoint (Days)															+/- 7 days	
	Screening (72 hours)	1 	2	3	4	5	7	9	12	14	16 	18 	21 	24 	28 		
		End of Treatment		60													
Informed Consent	X																
Medical and Surgical History 	X																
Demographics	X																
Physical exam 	X	X															
Chemistry	X	X	X	X	X	X	X	X	X	X	X	X	X	X	X	X	
Hematology	X	X	X	X	X	X	X	X	X	X	X	X	X	X	X	X	
Coagulation	X	X	X	X	X	X	X	X	X	X	X	X	X	X	X	X	
Urinalysis	X	X										X					
Pregnancy test	X	X															
12-lead ECG	X	X										X					
Chest X-ray	X	X															
Vital signs	X	X	X	X	X	X	X	X	X	X	X						
SBT Assessment		X	X	X	X	X	X	X	X	X	X						
Respiratory assessments	X	X	X	X	X	X	X	X	X	X	X						
Blinded Dosing 		X	X	X	X	X	X	X	X	X							
OSCI Status	X	X					X					X				X	
Adverse Events		X	X	X	X	X	X	X	X	X	X	X	X	X	X	X	
Concomitant Medication	X	X	X	X	X	X	X	X	X	X	X	X	X	X	X		
Follow-Up  (Telemed)															X	X	

1. History to include but not limited to any significant, ongoing, or controlled with treatment medical condition; date of hospital admission; date of ICU admission; start time of supplemental oxygen therapy; start time of nasal high-flow oxygen therapy; start time of non-invasive mechanical ventilation or mechanical ventilator via intubation.
2. If screening assessments are not completed prior to start of infusion, conduct on Day 1, prior to infusion. If performed as part of screening and within 72 hours, do not repeat unless required by the Investigator. Chest X-ray and Physical Exam do not need repeating within 24 hours.
3. Physical exam to include lung auscultation.
4. Continuous infusion of USB002 or placebo for up to 14 days.
5. Day 16 is also End of Treatment – all End of Treatment assessments are to be conducted at Day 16 or for any discharge prior to Day 16.
6. If subject is discharged from hospital, Telemed visits will be conducted once a week until Day 28, with the first occurring approximately 7 days after discharge. Day 28 and Day 60 Telemed visits will occur on Days 28 and 60, respectively, regardless of discharge date and timing of previous Telemed visits. Discharged subjects will not attend the site for visits (Days 18, 21, or 24, as applicable to discharge day) or undergo procedures regularly scheduled for those visits.
7. Telephone follow-up, if discharged. Day 28 phone call window = +/- 3 days; window not applicable if still hospitalized.

## 5.5. Concomitant Medication

Any treatment or medication for respiratory distress associated with COVID-19 infection, underlying medical conditions, or prophylaxis, to include, but not limited to prescribed medication, anticoagulants, corticosteroids, convalescent plasma, or VEKLURY® (remdesivir) is allowed on this study. For this study, a prescription medication is defined as a medication that can be prescribed only by a properly authorized/licensed clinician.

All concomitant medications will be recorded on the case report forms (eCRFs), to include concomitant prescription medications, over-the-counter medications, and non-prescription medications taken by, or administered to the subject while on study (ongoing at baseline, changed from baseline (frequency and/or dose), started after baseline) until discharge. Medication started after discharge will be collected only if administered for the treatment of a Serious Adverse event. Any medication continuing after discharge will be recorded as ongoing in the eCRF.

Medications that are needed for the purpose of mechanical ventilation i.e. any induction agents, muscle relaxants, or sedative agents are not needed to be captured. Medication administered for other procedures that might be performed while in ICU e.g. opiates/analgesics for tracheostomy, local anesthetics for chest tubes or other procedures, oral hygiene care, etc. are not needed to be captured. Anything that is administered for the treatment of COVID should be captured, as well as any vasopressors that might be required post infusion, (since there is the potential BP affect with USB002). Medication for complications of COVID e.g. prophylactic anticoagulation, DVTs, strokes, MIs, AKI, stroke, hemorrhage, etc. are captured. In addition, antibiotics used prophylactically or as treatment for any infection, and use of nephrotoxic agents, including any imaging agents, should be captured.

## 5.6. Prohibited Medication

Ongoing treatment of cancer with chemotherapy is not allowed while enrolled in the study. Use of vasopressors at time of infusion is not permitted.

# 6. ASSESSMENT OF SAFETY

## 6.1. Safety Parameters

Safety assessments to be conducted in this study include:

- AEs collected at all study visits from the time of first study drug dose;
- Changes in concomitant medications;
- Findings from physical examinations;
- Changes in laboratory parameters;
- Changes in respiratory and cardiovascular assessments.

Safety and tolerability will be assessed by the DSMB (see Section 6.6).

Any AE that is considered definitely, probably, or possibly related to USB002 is potentially a DLT. DLT will be defined per the DSMB SMP.

### **6.1.1. Definition of Adverse Events (AE)**

An AE is any untoward medical occurrence in a patient or clinical investigation subject administered a pharmaceutical product that which does not necessarily have a causal relationship with this treatment. An AE can therefore be any unfavorable and unintended change in structure, function, sign, or symptom temporally associated with the use of a medicinal product, whether related to the product. Undesirable changes in laboratory values should not be considered AEs unless they are considered symptomatic of a clinical condition or diagnosis, are evaluated as clinically significant, or require therapy. Worsening of a pre-existing condition is also considered an AE, as is the discovery of an abnormal finding during a physical exam (done per SOC) that was not included in the medical history. Clinical conditions attributable to disease progression will be considered AEs.

### **6.1.2. Definition of Serious Adverse Events (SAE)**

An SAE is any AE that meets at least one of following criteria:

- Is fatal;
- Is life-threatening; in the opinion of the Investigator, the subject was at substantial risk of dying at the time of the adverse event, or use or continued use of the medical product might have resulted in the death of the patient;
- Is a persistent or significant disability or incapacity;
- Requires hospitalization or prolongs an existing hospitalization. Hospitalization will be defined as such if > 24 hours, or a hospitalization that requires an intervention to treat emergent symptomatology (non-diagnostic);
- Exposure prior to conception or during pregnancy may have resulted in a congenital anomaly or birth defect in the child;
- Other important medical events not noted in events above, but may be considered a serious experience when, based upon appropriate medical judgment, may jeopardize the subject and may require medical or surgical intervention to prevent one of the outcomes as listed in #1-5 in this definition.

## **6.2 Classification of an Adverse Event**

### **6.2.1. Severity of Event**

Signs and symptoms will be graded by the Investigator as mild, moderate, severe, life-threatening, or fatal according to the following definitions:

- **Mild:** The AE is transient and does not interfere significantly with the subject's normal functioning level. The AE resolves spontaneously or may require minimal

therapeutic intervention;

- **Moderate:** The AE produces limited functional impairment and may require therapeutic intervention. The AE produces no sequelae;
- **Severe:** The AE results in significant impairment of function and may lead to temporary inability to resume the subject's normal life pattern. The AE produces sequelae which require prolonged therapeutic intervention;
- **Life-Threatening:** The AE results in life-threatening consequences, urgent intervention is indicated, urgent operative intervention is indicated, or the patient is at risk of death at the time of the event if immediate intervention is not undertaken;
- **Fatal:** The AE results in death.

Further, toxicities should be evaluated according to the NCI-CTCAE v5.0 criteria.

### 6.2.2. Relationship to Study Drug

The following five-point scale will be used by the Investigator to rate the relationship of the AE to the study drug:

- **Definitely related:** A clinical event (including laboratory test abnormality) occurring in a plausible time relationship to drug administration, and which cannot be explained by concurrent disease or other drugs or chemicals. The response to withdrawal of the drug (de-challenge) should be clinically plausible. The event must be definitively associated pharmacologically, using a satisfactory re-challenge procedure, if necessary;
- **Probably related:** A clinical event (including laboratory test abnormality) with a reasonable time sequence to administration of the drug, unlikely to be attributed to concurrent disease or other drugs or chemicals, and which follows a clinically reasonable response on withdrawal (de-challenge). Re-challenge information is not required to fulfill this definition;
- **Possibly related:** A clinical event (including laboratory test abnormality) with a reasonable time sequence to administration of the drug, but which could also be explained by concurrent disease or other drugs or chemicals. Information on drug withdrawal may be lacking or unclear;
- **Unlikely to be related:** A clinical event (including laboratory test abnormality) whose temporal relationship to drug administration makes a causal relationship improbable (e.g., the event did not occur within a reasonable time after administration of the trial medication) and in which other drugs or chemicals or underlying disease provides plausible explanations (e.g., the participant's clinical condition, other concomitant treatments);
- **Not related:** An event for which sufficient information exists to conclude that the etiology of the event is unrelated to the study drug. An alternative definitive etiology should be documented by the Investigator.

### **6.2.3. Expectedness**

Expectedness determination will be related to the study drug specifically. An event may be unexpected in the subject but that in itself does not qualify as unexpected; review against information available and provided for the study drug is what will determine expectedness.

Sponsor will be responsible for determining whether an AE is expected or unexpected. An AE will be considered unexpected if the nature, severity, or frequency of the event is not consistent with the risk information previously described for the study drug, in the protocol and within the Investigator Brochure.

### **6.3. Adverse Event Follow-Up**

AEs will be recorded throughout the study and will be coded using the Medical Dictionary for Regulatory Activities (MedDRA). AEs ongoing at the final study visit or early termination, must be followed until resolution or until the Investigator determines them to be stable and/or adequately managed.

Date and time of onset and resolution (if applicable) of all AEs will be documented.

All SAEs must be followed until the event resolves or, in the opinion of the Investigator, become stable.

The Sponsor will report any serious, unexpected and drug-related AE to applicable regulatory agencies and provide these reports to the clinical trial sites. The Investigator must promptly inform the IRB of such events and retain a copy of the notification in the Investigator Site File (ISF).

### **6.4. Reporting Procedures**

#### **6.4.1 Adverse Event Reporting**

AEs will be captured from the start of USB002/placebo infusion until Day 28 or hospital discharge, whichever occurs last. Any AEs ongoing at Day 28 (or discharge) will be followed/assessed up to the Day 60 Telemed visit. No new AEs will be collected following discharge. SAEs (new or ongoing) will be followed and/or collected until Day 60.

All AEs (whether attributable to the study drug) occurring during the study observed by the Investigator or reported by the subject will be recorded on the eCRF. The following information will be recorded for all AEs:

- Event: name/condition/diagnosis/description;
- Onset and resolution time and/or date;
- Severity;
- Relationship to study drug (assessment by staff trained and authorized to

diagnose);

- Action taken;
- Seriousness.

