#### 2.1.1 Primary Objectives and Endpoints

The primary objectives of safety and tolerability of USB002 will be evaluated for rate of occurrence and severity of AEs resulting from clinical changes (Visit 1/Day 1 to Day 28): cardiovascular parameters, to include blood pressure (BP), heart rate (HR), 12-lead electrocardiogram (ECG), and requirements for inotropes and vasopressors; laboratory parameters, to include kidney and liver function.

The primary endpoint of preliminary efficacy will be demonstrating the difference between USB002 and placebo groups in time to peripheral capillary oxygen saturation ( $\text{SpO}_2$ )  $\geq 94\%$ , sustained for at least 48 hours, on room air through Day 28.

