If a subject's treatment is terminated after the Visit 1/Day 1 infusion begins, for any reason, all attempts will be made to conduct all remaining study visits and assessments,

as applicable (See Tables 2 and 3). End of Treatment (Part 1 – Visit 5; Part 2 – Day 16) procedures may be conducted during the 24-hour observation period. Missed End of Treatment assessments due to disease progression or early discharge, will be considered deviations.

Respiratory evaluations will be determined by recovery landmarks of time to acceptable spontaneous breathing efforts (up to 30 minutes), termination for the need of oxygen (see Spontaneous Breathing Trial [SBT]: Appendix 2), and time to discontinuation of ventilatory assistance, if applicable. Clinical status will be evaluated using the OSCI and physical examination findings.

Follow-up for AEs with a start prior to Day 28 will be followed to resolution, stabilization, or to Day 60. Survival will be captured during the follow-up period through to Day 60, regardless of treatment or hospitalization status. AEs with a start date after Day 28 will not be captured. Any SAE that occurs at any time, through to Day 60, will be collected.

Participation will terminate for all subjects on Day 60 or at early termination due to death, consent withdrawal or lost to follow-up.

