#### **Days 18, 21, 24, 28**

- OSCi assessment (Day 28);
- AEs;
- Laboratory (chemistry, hematology, coagulation and urinalysis per Section 5.2) (Day 21 and Day 28 with urinalysis at Day 28)
- Concomitant medications;
- Follow-Up (Telemed) (Day 28).

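### Protocol 6.4.1 and Section 3 give conflicting end dates for new non-serious AEs, and the SAP's TEAE rule and AE tables apply no end date

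*Protocol*

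**What the plan says.** Three protocol sentences bear on when collection of new non-serious AEs ends.

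- Protocol 6.4.1, opening sentence: capture runs from the start of infusion "until Day 28 or hospital discharge, whichever occurs last".
- Protocol 6.4.1, same paragraph: "No new AEs will be collected following discharge".
- Protocol Section 3, under Parts 1 and 2: "AEs with a start date after Day 28 will not be captured".

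SAEs are handled separately and run to Day 60 in Section 3, 6.4.1 and 6.4.2.

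The primary safety objective (Protocol 2.1.1, repeated in SAP 3.1) is the "rate of occurrence and severity of AEs resulting from clinical changes (Visit 1/Day 1 to Day 28"). Two other protocol statements are looser: "AEs collected at all study visits from the time of first study drug dose" (6.1) and "AEs will be recorded throughout the study" (6.3). Subjects discharged before Day 28 have weekly Telemed contacts until Day 28, and "Data from the Telemed visits post-discharge will be captured in the EDC" (5.4.5).

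In the SAP, the TEAE derivation (7.2) sets a lower bound at first infusion and no upper bound. The AE tables (8.2.1) report counts and frequencies of events and of subjects with events, with no cut-off day. SAP 8.1 asks for all outcomes to be summarised for total USB002 against total placebo, as well as by dose level.

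**The concern.** AEs are part of the primary safety endpoint. If new non-serious AEs stop being collected at discharge, each subject's observation time is set by the discharge day. Time to discharge is a secondary efficacy endpoint (SAP 4.3). A group that goes home sooner would then show fewer non-serious TEAEs at the same true event rate, and a reader of the pooled table could not tell fewer events from less observation.

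The planned exposure summaries would not reveal this. SAP 7.2 measures time in trial from consent to study completion or withdrawal, and time on treatment from first to last infusion. Neither is AE follow-up time. Capture that ended at discharge would also fall short of the Day 1 to Day 28 window that both documents name in the objective.

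**Working it through.** **Step 1: the three rules side by side.** Let D be the discharge day. Rule A (6.4.1, opening sentence) ends capture at max(28, D). Rule B (6.4.1, discharge sentence) ends it at D. Rule C (Section 3) ends it at Day 28 onset.

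| D | A | B | C | Conflict |
|---|---|---|---|---|
| 10 | 28 | 10 | 28 | B against A and C, 18 days |
| 28 | 28 | 28 | 28 | none |
| 40 | 40 | 40 | 28 | C against A and B, 12 days |

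The rules agree only when D = 28.

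**Step 2: observation lost under Rule B.** The share of the 28-day window lost is 1 − D/28: 75% for D = 7, 50% for D = 14, 25% for D = 21. These discharge days are illustrative. Lost calendar time is not the same as lost events.

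**Step 3: possible size in the pooled table.** The documents give no AE rates or discharge days, so these inputs are assumptions:

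- Starting hazard h of 0.05 to 0.10 non-serious AEs per day.
- One arm discharged on Day 7, the other on Day 14.
- n = 10 per arm. Three full cohorts give 9 per arm, and Cohort 4 adds 3 subjects whose split is not stated.
- Poisson counts.

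The expected count to day D is n·h·D for a constant hazard, or n·h·(1 − e^(−kD))/k with k = ln 2/half-life for a falling one. The SD of the difference is the square root of the sum of the two means.

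| Hazard | Expected counts, D = 7 vs 14 (h = 0.05; h = 0.10) | Difference | SD |
|---|---|---|---|
| Constant | 3.5 vs 7.0; 7.0 vs 14.0 | 3.5; 7.0 | 3.24; 4.58 |
| Half-life 7 d | 2.52 vs 3.79; 5.05 vs 7.57 | 1.26; 2.52 | 2.51; 3.55 |
| Half-life 3.5 d | 1.89 vs 2.37; 3.79 vs 4.73 | 0.47; 0.95 | 2.06; 2.92 |

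Only the constant-hazard row exceeds one SD (3.5/3.24 = 1.1; 7.0/4.58 = 1.5). The same holds with n = 9 (3.15 and 6.30 against 3.07 and 4.35) and n = 12 (4.20 and 8.40 against 3.55 and 5.02). With a four-day gap (Day 10 against Day 14), n = 10 and a constant hazard, the difference is 2.0 to 4.0 against an SD of 3.46 to 4.90, below one SD. With 3 subjects per group at a single dose, even the constant case (1.05 to 2.10 against 1.77 to 2.51) stays below one SD.

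**Step 4: would a per-day rate repair it?** Day 7 against Day 14 gives count ratios of 0.50 (constant), 0.667 (half-life 7 d) and 0.80 (half-life 3.5 d). Follow-up differs by a factor of 2, so the per-day rate ratios are twice these: 1.00, 1.33 and 1.60. The rate is right only under a constant hazard. Under a falling hazard it over-corrects against the group discharged sooner.

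**The case against.** **6.4.1 can be reconciled with itself.** The discharge sentence may refer back to the later-of end point, so that it bars new AEs only once both Day 28 and discharge have passed. That is a fair reading, but the reader must supply it because the sentence carries no such limit. It also leaves the conflict with Section 3 for stays beyond Day 28.

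**The rest of the protocol does not settle the matter.** A reader might infer that the surrounding text clearly requires collection to Day 28. It does not. Sections 5.4.2 and 5.4.3 tie daily AE review to hospitalisation. The AE entry beside the Day 28 Telemed contact proves little, because Day 60 has the same entry although Section 3 bars new non-serious AEs by then. The statements in 6.1 and 6.3 would, taken literally, run to Day 60. Section 5.4.5 says that Telemed data are entered, not that new AEs are solicited. The firmest support for Day 28 is the objective itself.

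**Little is at stake.** Part 1 infusion lasts at most 96 hours, followed by 24 hours of observation. Protocol 1.5 infers a half-life of about one hour from subcutaneous data (a different route), so events after discharge would be largely off drug. Escalation uses 96-hour data, SAEs run to Day 60, and the SAP plans no inference. AEs and days to discharge are both listed. All of this stands and limits the severity. It does not supply an end date for the primary safety tables.

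**A hard cut at Day 28 would discard events** validly recorded in long-stay subjects under the later-of rule. This stands, and the fix lists such events instead of dropping them.

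**Conclusion.** The inconsistency is real and should be corrected, but its likely effect is small. The protocol's end dates for new non-serious AEs agree only for discharge on Day 28, and the SAP's TEAE rule and AE tables apply none.

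Three stronger conclusions are tempting and not supported:

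- A reader might infer that the SAP has no AE window at all. SAP 3.1 names Day 1 to Day 28; the gap is that 7.2 and 8.2.1 do not carry it through.
- A reader might infer that non-serious AEs were lost or that the arms are already biased. The documents do not show which sentence sites followed or when subjects were discharged.
- A reader might infer that SAEs or dose escalation are compromised. SAE collection runs to Day 60, and escalation reviews use 96-hour data.

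What is exposed is the reading of one descriptive comparison, pooled USB002 against pooled placebo for non-serious TEAEs, in 21 subjects. The artefact exceeds one chance SD only in the pooled scenario with a constant hazard and a seven-day gap in discharge. That result rests on assumed AE rates, discharge days, arm sizes and Poisson variation.

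**What to change.** 1. Reconcile Protocol Section 3 and 6.4.1 to one end date that matches the objective: new non-serious AEs with onset through Day 28 whatever the discharge date, using the Telemed contacts already scheduled in 5.4.5, and SAEs through Day 60.
2. In SAP 7.2 and 8.2.1, apply the same cut-off to non-serious TEAE summaries and keep serious and fatal TEAEs through Day 60. List any later non-serious events.
3. In the report, state which window was actually applied to the 21 subjects. If capture stopped at discharge for any of them, show AE follow-up days by pooled arm beside the counts. If per-day rates are added, note that they over-correct when the hazard falls with time.

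An early fixed-window table by Study Day is optional and not part of the fix.

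The cost is a few lines of protocol and SAP text, one report sentence and at most one extra table. Enrolment has stopped, so the protocol edit cannot recover data already missed; the practical value lies in the SAP and the report. Telephone contact also detects fewer AEs than daily in-hospital review, particularly those found through vital signs, ECG or laboratory tests. A common end date therefore improves ascertainment without making it equal, and the report should say so.
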